2.4.4.2 Analyses of secondary efficacy endpoints

2.4.4.2.1 Time to first clinical relapse after enrollment of open-label period up to the end of open-label period

The first clinical relapse occurring from enrollment of open-label period to the end of the open-label period will be included for analysis. Hazard ratio with associated 95% confidence interval, Kaplan-Meier estimates and its 95% confidence interval will be presented using the same method as described in [Section 2.4.4.1](#). A stratified log-rank test with time to first clinical relapse as the dependent variable, treatment group as a test variable, region (definition of the regions are provided in [Section 2.5.5](#)), and pubertal status as covariates will be provided.

Censoring rule

If a patient has no clinical relapse after enrollment in open-label period and before treatment discontinuation/completion in the open-label period, the patient will be considered as free of relapse till the date of last IMP administration reported on the EOT page. If this date is missing, last dose date on the IMP administration page will be used.

Given that confirmation of relapse in the open-label period is based on objective neurological examinations, it is possible that a patient remained on treatment but did not perform any objective neurological examinations due to Covid-19 pandemic. If a patient reported suspected MS relapse and had no objective neurological examinations assessed afterwards due to the pandemic, the censor date will be the date of the last EDSS or FSS assessment.

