EOT = end of treatment (EOT= First visit after last study drug intake), EDSS = expanded disability status scale, FS = functional score, BVMTR = brief visuospatial memory test-revised, SDMT=symbol digit modalities test, MRI = magnetic resonance imaging, PK = pharmacokinetic

- a Recommended windows: The window for obtaining biological samples at any given visit will be ±7 days. All other treatment period assessments should be completed within ±7 days of the scheduled visit date relative to the randomization visit. Post drug elimination follow-up visits should be ±7 days of scheduled visit relative to end of treatment.
- b Randomization visit up to 28 days from signing of informed consent.
- c End-of-treatment and premature discontinuation visit. This visit does not need to be performed when the patient switches to the open label period after a confirmed relapse or high MRI activity (as per protocol criteria). The drug elimination procedure must be initiated at this visit if applicable.

- d* For discontinuing treatment, 2 post drug elimination follow up visits should be scheduled 2 weeks and 4 weeks after study medication discontinuation and initiation of the drug elimination procedure. All patients who prematurely and permanently discontinue study medication will be asked to continue until the planned end of double-blind period.
- e* Re-consent must follow any RAP confirmed MS relapse for continuing in study when occurrence during PK run-in, for switching into open-label period when occurrence after PK run-in.
- f* To be prescribed at Visit 1 and report checked at Visit 2. MRI scan performed within 6 weeks prior to randomization can be used as the baseline MRI if performed according to the operations manual and accepted by the central reader.
- g* During the adverse event reporting process, specific questions about pulmonary symptoms and peripheral neuropathy symptoms will be asked. (Patients will be instructed to alert the treating physician of symptoms suggestive of immunodeficiency).

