1.4 STUDY PLAN

The study design is briefly described in the following graphical presentation:

R: Randomization

Note: An optional additional extension period with teriflunomide is offered to young patients when they complete the study, to provide treatment until they are 18 years old and/or can switch to commercial product, whichever comes first.

Table 1 - Study schedule for the double-blind period

Variable	Visit
Brain MRI	Screening, Weeks 24, 48, 72 and Week 96/end of treatment (EOT) ^a visit, Week 36 if necessary
EDSS	Screening, randomization, Weeks 24, 48, 72, Week 96/EOT ^a visit, and unscheduled relapse visits
SDMT	Randomization, Weeks 24, 48, 72, and Week 96/EOT ^a visit,
Cognitive Battery Test	Randomization and EOT ^a visit
Clinical Laboratory	Screening, randomization, every 4 weeks up to 24 weeks and then every 6 weeks up to the Week 96/EOT ^a
Vital signs	Screening, randomization, Weeks 4, 8, 12, 24, and every 12 weeks up to Week 96/EOT ^a visit
ECG	randomization, Week 96/EOT ^a and after EOT ^a if abnormality
Immunoglobulins and TSH	Randomization, Weeks 24, 48, 72 and Week 96/EOT ^a visit
PK	Weeks 2, 3, 4, 8, 12, 24, 36 and Week 96/EOT ^a visit
Physical examinations	Screening, randomization, Weeks 12, 24, and every 12 weeks up to Week 96/EOT ^a visit
Tanner assessment	Randomization, at Week 24, 48, 72, and at Week 96/EOT ^a for all patients (until complete sexual maturity).

^a Patients who complete the double-blind treatment period or who prematurely discontinue, should complete EOT visit.

Table 2 - Study schedule for the open-label period

Variable	Visit
Brain MRI	Weeks 48, 96, 144 and Week 192/end of treatment (EOT) ⁰ visit
EDSS	Weeks 24, 48, 72, 96, 120, 144, 168, Week 192/EOT ⁰ visit, and unscheduled relapse visits
SDMT	Weeks 24, 48, 72, 96, 120, 144, 168, Week 192/EOT ⁰ visit
Cognitive Battery Test	Week 96 and Week 192/EOT ⁰ visit
Clinical Laboratory	Transition, Weeks 4, 12, and then every 12 weeks up to the Week 192/EOT ⁰
Vital signs ^b	Transition, Weeks 4, 8, 12, and then every 12 weeks up to the Week 192/EOT ⁰
ECG	Week 192/EOT ⁰ and after EOT ⁰ if abnormality on EOT or ECG could not be performed at EOT (in exceptional circumstances).
Immunoglobulins and TSH	Week 96 and Week 192/EOT ⁰ visit
PK	Weeks 2, 3, 4, 8, 12, 24, 36 and Week 192/EOT ⁰ visit
Physical examinations	Weeks 12, 24, and then every 24 weeks up to the Week 192/EOT ⁰

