If a patient has no clinical relapse after randomization in double-blind period and before treatment discontinuation/completion in the open-label period, the patient will be considered as free of relapse till the date of last IMP administration reported on the EOT page. If this date is missing, last dose date on the IMP administration page will be used.

Given that confirmation of relapse in the open-label period is based on objective neurological examinations, it is possible that a patient remained on treatment but did not perform any objective neurological examinations due to Covid-19 pandemic. If a patient reported suspected MS relapse and had no objective neurological examinations assessed afterwards due to the pandemic, the censor date will be the date of the last EDSS or FSS assessment.

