2.4.4.3 Analysis of additional efficacy endpoint

2.4.4.3.1 Annualized relapse rate

The annualized relapse rate (ARR) is defined as the number of confirmed clinical relapses occurred during the study per patient-year. It will be analyzed in open-label period only. A confirmed clinical relapse is defined as the appearance of a new clinical sign/symptom or clinical worsening of a previous sign/symptom (one that had been stable for at least 30 days) that persists for a minimum of 24 hours in the absence of fever. Each episode of relapse must be confirmed by the treating neurologist, based on the objective assessments by an independent evaluator (the examining neurologist) by documenting either of the following:

- A) A 1-point increase in at least two FS functions, or a 2-point increase in at least one FS function (excluding bowel/bladder and cerebral) from the previous clinically stable assessment, or;
- B) An increase of at least 0.5 point in EDSS score (unless EDSS=0, then an increase of at least 1.0 point is required) from the previous clinically stable assessment.

Relapses are collected on CRF page “MS relapse”. The objective confirmation, based on the protocol-defined criteria, is reported (Yes/No) in the CRF. Only confirmed clinical relapses will be used in the analysis.

A gross estimate of annualized relapse rate for a treatment group would be the total number of relapses for patients in the treatment group divided by the sum of standardized study durations for patients in the treatment group. Total number of confirmed clinical relapses and standardized study duration will be calculated for each patient.

- Total number of confirmed clinical relapses is defined as the number of confirmed clinical relapses with onset between enrollment date of the open-label period and treatment discontinuation/completion date (same as last dose IMP intake date).
- Standardized study duration (in year) will be calculated by (last dose IMP intake date - enrollment date of the open-label period + 1) / 365.25.

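### A suspected open-label relapse left unexamined because of Covid-19 triggers back-dated, informative censoring with no floor at open-label entry, and the annualized relapse rate has no matching rule

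*SAP*

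**What the plan says.** The default in both time-to-first-relapse analyses (SAP 2.4.4.1 and 2.4.4.2.1) is that, without a relapse, "the patient will be considered as free of relapse till the date of last IMP administration reported on the EOT page". Version 2 of the SAP added a Covid-19 exception, worded identically in both sections: "If a patient reported suspected MS relapse and had no objective neurological examinations assessed afterwards due to the pandemic", then "the censor date will be the date of the last EDSS or FSS assessment".

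The secondary endpoint starts its clock at open-label entry: "The first clinical relapse occurring from enrollment of open-label period to the end of the open-label period will be included for analysis". The open-label EDSS schedule in SAP Table 2 is "Weeks 24, 48, 72, 96, 120, 144, 168" and Week 192/EOT, with nothing at the transition visit. The end-of-treatment visit of the double-blind period includes an EDSS, but Protocol 1.2 (footnote c) says of it: "This visit does not need to be performed when the patient switches to the open label period after a confirmed relapse or high MRI activity".

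For the annualized relapse rate (SAP 2.4.4.3.1), the numerator is restricted: "Only confirmed clinical relapses will be used in the analysis". The denominator runs from open-label enrollment to last dose: "Standardized study duration (in year) will be calculated by (last dose IMP intake date". SAP Table 3 limits the Covid-19 change to time-to-event endpoints and the open-label end-of-treatment window.

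Protocol 11.4.4.1 plans a double-blind sensitivity analysis that counts relapses whether or not they were confirmed. SAP Appendix B lists no open-label counterpart. Protocol Appendix G (17.7) leaves methods for emergency-related missing efficacy data to the SAP.

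**The concern.** Two patients with equally sparse examinations are treated differently. The one who reports nothing stays at risk, event-free, to last dose. The one who reports a suspected relapse loses the event and also the follow-up back to the last EDSS or FSS. Removal from the risk set therefore depends on the outcome, which violates the non-informative censoring that Cox and Kaplan-Meier methods need.

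Two further gaps follow. The censor date in 2.4.4.2.1 has no lower limit at the time origin. The annualized rate also drops the event but keeps all the exposure, so the time-to-event and rate analyses disagree about the same patient. The Kaplan-Meier relapse-free proportions in 2.4.4.2.2 rest on the same relapse data.

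**Working it through.** **1. The rule applied to records** (open-label days, day 1 = first dose).

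- *Late in the open-label period.* Last EDSS at Week 72, relapse reported by phone at Week 90, end-of-treatment visit remote. The time-to-event record is censored at Week 72, losing the event and (90 − 72) × 7 = 126 days of follow-up. The annualized rate records 0 relapses over 672/365.25 = 1.84 years.
- *96-week completer.* The transition visit generally coincides with the double-blind end-of-treatment visit. With a suspected relapse before the first open-label EDSS and no later examination, the time in 2.4.4.2.1 is about 0.
- *Switcher after a confirmed relapse.* If the last EDSS was at the relapse visit, 14 days before open-label entry (assumed), the time is −14 days and cannot enter a risk set.

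**2. Whether the calendar allows the last two cases.** Enrolment was complete by 02-Aug-2018 (Protocol Appendix I, reason for amended protocol 3), so open-label entry could run to 02-Aug-2018 + 96 weeks = 04-Jun-2020. The Covid-19 memos start on 21-Feb-2020 (China) and 24-Mar-2020 (global).

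| Suspected relapse at | Entry no earlier than (China / global) | Minimum time double-blind if randomized 02-Aug-2018 |
|---|---|---|
| Open-label Week 24 | 06-Sep-2019 / 08-Oct-2019 | 400/7 = 57 / 432/7 = 62 weeks |
| Open-label Week 12 | 29-Nov-2019 / 31-Dec-2019 | 484/7 = 69 / 516/7 = 74 weeks |

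The zero or negative time is therefore possible for completers and late switchers. It is not possible for a patient who switched at, say, Week 36: entry by 11-Apr-2019 puts open-label Week 24 in September 2019, before the measures began.

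**3. Size.** The planning hazards reproduce: −ln(1 − 0.60)/2 = 0.4581 per year for placebo, and half of that is 0.2291 for teriflunomide. The illustration uses 0.2291. It assumes 96 weeks of open-label follow-up, EDSS every 24 weeks, exponential relapse times, and k real first relapses left unexamined among N patients. N = 100 to 165 and k = 1 to 5 are assumptions; the documents give neither.

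| N, k | 96-week relapse probability, all counted | SAP rule | Censored at reported onset instead |
|---|---|---|---|
| 165, 1 | 34.4% | 34.0% | 34.0% |
| 100, 5 | 34.5% | 30.6% | 30.4% |

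For N = 100, k = 5 the estimated hazard is 0.232 with all events, 0.200 under the SAP rule and 0.198 with censoring at onset.

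For the annualized rate, expected relapses are 0.2291 × N × 96/52.18, which is 69.5 for N = 165 and 42.1 for N = 100. The fall is 1/69.5 = 1.4% and 5/42.1 = 11.9%.

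The last column matters for the fix. Censoring at onset removes the same events and restores event-free time, so the estimates move slightly further down.

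**The case against.** The trigger is narrow. It needs a suspected relapse and no objective examination at any later time because of the pandemic, while Memo 19 (Protocol 17.8.2) provides for deferred or unscheduled EDSS. Open-label efficacy is exploratory by SAP 2.4.4 and 2.4.4.4, both groups receive teriflunomide, and the double-blind primary analysis has its own SAP. Relapses are recorded with a confirmation field, so affected cases can be found. All of this stands and limits the weight of the point.

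A reader might infer more than the documents support:

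- *That any later routine EDSS makes the patient relapse-free to last dose.* The criteria in 2.4.4.3.1 compare with the last clinically stable assessment and set no time limit, so a deferred examination can still confirm the relapse. If it does not, the absence of an event follows from the requirement for objective findings.
- *That one patient is handled three ways across three endpoints.* The two time-to-event sections share one rule, so the split is between time-to-event and the annualized rate. A switcher after a confirmed relapse already has an event in the analysis from randomization, and the Covid-19 rule never reaches that patient there.
- *That back-dating is the source of the bias.* It loses follow-up. The bias comes from dropping the event.
- *That the rate is understated by a known share.* No document gives the share of relapses left unexamined, and some suspected relapses would not have been confirmed.

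**Conclusion.** The point holds for the exploratory open-label relapse endpoints. The Covid-19 rule is informative because the suspected event triggers it, and it lowers relapse probability and hazard to the extent that those relapses are real. It can produce a time of about zero for completers and a negative time for late switchers in 2.4.4.2.1. It is not matched in the annualized rate.

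The effect is probably small. Under the stated assumptions it ranges from 0.4 to 3.9 percentage points of 96-week relapse probability and from 1.4% to 11.9% of the annualized rate. It should be smaller for the endpoint from randomization, where relapses already confirmed in the double-blind period still count. The number affected is not given and the direction of any between-group bias is unknown. Nothing here bears on the double-blind primary result.

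**What to change.** 1. Add one sensitivity analysis for both time-to-first-relapse endpoints and the annualized rate, counting each suspected but unexamined relapse as an event at its reported onset. Label it an upper bound, since some would not have been confirmed. It mirrors the double-blind analysis of relapses confirmed or not, and it is the change that addresses the bias.
2. State in 2.4.4.2.1 that the censor date is never before open-label enrollment.
3. Use one rule for these patients in the main time-to-event and annualized-rate analyses, ending annualized-rate exposure at the same date as the time-to-event censoring.
4. Report the number of such patients by group.

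Moving the censor date to reported onset would recover follow-up and is defensible, but it should not be presented as the remedy for the bias. The cost is SAP wording and one additional run. The MS relapse CRF page already records relapses with a confirmation field, and the annualized rate already uses onset dates.

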2.4.4.2.2 The proportion of clinical relapse-free patients

The proportion of patients with clinical relapse-free at Weeks 24, 48, 72, 96, 120, 144, 168 and 192 will be estimated based on Kaplan-Meier methods. The complementary log-log transformation will be used to construct 95% confidence intervals. A Kaplan-Meier graph summarizing the event probability over time will be presented.

2.4.4.2.3 Magnetic resonance imaging (MRI) variables

General rules for MRI variables

The protocol requires that the MRI should not be performed until after a minimum of 14 days following completion of corticosteroid therapy. Thus, MRI values obtained within 14 days of systemic corticosteroid therapy will be excluded from the analysis.

Baseline for MRI variables is defined as the last non-missing, valid MRI value that was measured before or on the day of first administration of IMP in the double-blind period. A previous MRI performed in the 6 weeks preceding randomization could be used as the baseline if performed according to the specifications for this study. For valid MRI values in subsequent post baseline visits, time windows (see [Table 4](#) and [Table 5](#) in [Section 2.5.3](#)) between visits will be used to capture MRI measurements. For multiple records within a visit window, the one closest to the targeted visit date will be used.

Number of lesions

The number of new or enlarged T2 lesions per MRI scan will be analyzed using a negative binomial regression model with robust variance estimation. The model will include the total number of new or enlarged T2 lesions as the response variable, with treatment group, region, pubertal status and age as covariates. In order to account for different numbers of MRI scans performed among patients, the log-transformed number of scans will be included in the model as an offset variable. The robust error variances can be estimated by specifying the patient identifier in the repeated statement using SAS PROC GENMOD. The estimated number of lesions per scan and associated 2-sided 95% confidence interval (CI) will be provided for each treatment group.

The number of T1 Gd-enhancing lesions per MRI scan and the number of new T1 hypointense lesions per MRI scan will be analyzed using a similar negative binomial regression model as described above for T2 lesions.

Volume of lesions and brain

Descriptive statistics of the change from baseline in volume of T2 lesions, T1 hypointense lesions and the percentage change of brain volume in the original scale will be summarized at each visit by treatment group.

The proportion of patients free of new or enlarged T2 lesions

The proportion of patients free of new or enlarged T2 lesions at Weeks 48, 96, 144 and 192 will be summarized based on all patients having an MRI at these time points. Kaplan-Meier methods will be used for estimation.

Censoring rule

If a patient has no new or enlarged T2 lesions detected by MRI scan before treatment discontinuation/completion in the open-label treatment period, the patient will be considered as free of new or enlarged T2 lesions till the date of last during-treatment MRI assessment. The last during-treatment MRI assessment is defined as last MRI assessment before treatment discontinuation/completion in the treatment period. In rare cases, if a patient had a delayed MRI scheduled during the open-label period but performed after the open-label EOT visit due to the Covid-19 pandemic, then the delayed MRI result will be considered in the open-label analysis. This MRI assessment is considered as during-treatment assessment.

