	

• Patients experiencing a relapse after the PK run-in period (8 weeks) and if confirmed by the Relapse Adjudication Panel (RAP) or high MRI activity as defined below or completing the 96-week period will have the option to continue in the open label period.

• Evaluation of high MRI activity

1) If 5 or more new/enlarged T2 lesions at Week 24, an additional MRI will be performed at Week 36.

2) Criteria for high MRI activity to qualify for switch to open label treatment:

• At least 9 new/enlarged T2 lesions at Week 36 or

• At least 5 new/enlarged T2 lesions on each of 2 consecutive MRI scans at Week 36 and Week 48, or at Week 48 and Week 72. (Note: new/enlarged since previous scan)

 
Open-label period:
 
The open-label period will follow the double-blind period and last until 192 weeks after randomization. Its duration for a given patient will depend on when the patient enters this period. The duration of the open-label period will be 96 weeks for patients completing the 96-week double-blind period on treatment, and longer for patients switching to open-label during the initial 96 week double-blind period at the occurrence of a confirmed relapse or in case of high MRI activity.
 
It includes a blinded PK run-in phase (8 weeks, similarly to the double-blind period).
 
Optional additional extension period for young patients:
 
A treatment extension period with teriflunomide will be proposed to patients too young to access commercialized teriflunomide as per authorized indication when completing the 192-week treatment period, until they become adult or until they are able to switch to commercial product, whichever comes first.
 
Follow up period for patients who discontinue:
 
Upon discontinuation of the study treatment (either by early termination or not), patients who will not be treated with teriflunomide post-study will be required to perform an accelerated elimination procedure within a 4 week follow up period.
 
Two Clinical Study Reports (CSR) will be issued:
 

• The first CSR will report the final analysis of the double-blind treatment period. The study methods described in this document primarily relate to this treatment period and analysis.

• The second CSR will report the analysis of the open-label data at the conclusion of the extension period for all included patients.

 
The data for the optional additional extension period for young patients will be reported separately.

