#### **MRI**

All brain scans will be reviewed and interpreted by one or more neuroradiologists at an independent, central facility with no access (ie, blinded) to treatment assignment thereby avoiding bias.

An MRI manual explaining the instructions for standard image acquisition requirements, data transfer, archiving and shipping, and outlining the phantom data approval process will be provided to all centers.

MRI should not be conducted within 2 weeks of steroid administration due to potential interference.

In case of at least 5 new/enlarged T2 lesions at the MRI of Week 24, an additional MRI will be performed at Week 36.

Then, in case of:

- At least 9 new/enlarged T2 lesions at Week 36, or,
- At least 5 new/enlarged T2 lesions on each of the 2 consecutive MRI scans of Week 36 and Week 48, or,
- At least 5 new/enlarged T2 lesions on each of the 2 consecutive MRI scans of Week 48 and Week 72.

Patients will have the option to continue in an open label teriflunomide treatment arm.

(Note: new/enlarged refer to previous scan)

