2.5.3 Windows for time points

Time window for MRI measurements and SDMT will be used to capture data collected between visits. It is defined in [Table 4](#) and [Table 5](#). Baseline values will be the baseline defined in the double-blind period of the study. All days in the visit window tables for double-blind period ([Table 4](#) and [Table 6](#)) and the open-label period ([Table 5](#) and [Table 7](#)) are relative to the first dose date in each period respectively.

Table 4 - Visit window for MRI variables and SDMT in the double-blind period

Week	Visit	Target day	Schedule A^a	Schedule B^b
0	Baseline	1	Up to 1st dose date	Up to 1st dose date
24	Visit 8	169	after 1 st dose date - 252	after 1 st dose date -210
36	Visit 10	253	Not applicable	211 - 294
48	Visit 12	337	253 - 420	295 - 420
72	Visit 16	505	421 - 588	421 - 588
96	Visit 20	673	589 - Last double-blind dose date + 60 days and before 1st open label dose	589 - Last double-blind dose date + 60 days and before 1st open label dose

^a SDMT and MRI variables for patients without MRI assessment for Week 36

^b MRI variables for patients with MRI assessment for Week 36

Table 5 - Visit window for MRI variables and SDMT in the open-label period

Week	Visit	Target day	SDMT	MRI variables
0	OL transition visit	1	Up to the first dose in OL period	Up to the first dose in OL period
24	OL Visit 7	169	after 1st open-label dose date - 252	Not applicable
48	OL Visit 11	337	252 - 420	after 1st open-label dose date – 504
72	OL Visit 15	505	421 – 588	Not applicable
96	OL Visit 19	673	589 – 756	505 – 840
120	OL Visit 23	841	757 – 924	Not applicable
144	OL Visit 27	1009	925 – 1092	841 – 1176
168	OL Visit 31	1177	1093 – 1260	Not applicable
192	OL Visit 35	1345	1261 - Later of the Last open-label visit date or the 1st dose date in optional additional extension period	1177 - Later of the Last open-label visit date or before 1st dose date in optional additional extension period

For multiple records within a visit window, the one closest to the targeted visit date will be used.

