Week (W) ^a	W102	W108	W114	W120	W126	W132	W138	W144	W150	W156	W162	W168	W174	W180	W186	W192/ EOT ^{b, u}	EOT +2W	EOT +4W	Relapse visit
Visit number ^r	20	21	22	23	24	25	26	27	28	29	30	31	32	33	34	35	36 ^c	37 ^c	
Treatments																			
Concomitant medications	X	X	X	X	X	X	X	X	X	X	X	X	X	X	X	X	X	X	X
Dispense study drugs/IVRS call		X		X		X		X		X		X		X		X ^t			
Accountability/co compliance		X		X		X		X		X		X		X		X			
Teriflunomide PK sampling ^k																X	X ^l	X ^l	

EOT = end of treatment (EOT= First visit after last study drug intake), EDSS = expanded disability status scale, FS = functional score, BVMTR = brief visuospatial memory test-revised, SDMT=symbol digit modalities test, MRI = magnetic resonance imaging, PK = pharmacokinetic.

- a The open label period starts by the transition visit. It is recommended that there is no time gap between the 2 periods, or as short as possible and if possible less than 2 weeks. In case of start of the open label period at the end of the 96 weeks of the double-blind period, the transition visit will generally coincide with the EOT visit of the double-blind period. Recommended windows: The window for obtaining biological samples at any given visit will be ±7 days. All other treatment period assessments should be completed within ±7 days of the scheduled visit date relative to the transition visit. Post drug elimination follow-up visits should be ±7 days of scheduled visit relative to end of treatment.
- b End-of-treatment and premature discontinuation visit.
- c For patients discontinuing treatment, 2 post drug elimination follow up visits should be scheduled 2 weeks and 4 weeks after study medication discontinuation and initiation of the drug elimination procedure. When applicable patients who prematurely and permanently discontinue study medication will be asked to continue until the planned end of double-blind period (ie, 96 weeks after randomization).
- d Re-consent before starting open-label period and after confirmed MS relapse and when patients turn adults as per local regulations.
- e During the adverse event reporting process, specific questions about pulmonary symptoms and peripheral neuropathy symptoms will be asked. (Patients will be instructed to alert the treating physician of symptoms suggestive of immunodeficiency).

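### Keeping one closest-to-target scan per window discards new lesions seen on other scans, including the open-label EOT scan of some switchers, and can class a patient with new T2 lesions as lesion-free

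*SAP*

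**What the plan says.** The number of new or newly enlarged T2 lesions is a key secondary imaging endpoint (SAP 2.1.3.2). The only reference scan that the documents give for it is the previous one: Protocol 8.1 (MRI) has "Note: new/enlarged refer to previous scan" and the Clinical Trial Summary has "Note: new/enlarged since previous scan". Both notes stand beside the criteria for switching to open label.

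SAP 2.4.4.2.3 sets two rules for all MRI variables. First, "MRI values obtained within 14 days of systemic corticosteroid therapy will be excluded from the analysis". Second, "For multiple records within a visit window, the one closest to the targeted visit date will be used". SAP 2.5.4 sends unscheduled scans through the same windows. For the count model, "The model will include the total number of new or enlarged T2 lesions as the response variable" and "the log-transformed number of scans will be included in the model as an offset variable".

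T2-free status (SAP 2.4.4.2.3) and disease-free status (SAP 2.4.4.2.6) use the same lesion information. No rule adds an unretained scan's lesions to the next count, has the next scan re-read against the last retained one, or states that lesion-free status uses every scan.

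**The concern.** Choosing one scan per window is harmless for a volume, where the retained scan stands on its own. An incident count describes the interval since its reference scan. If an intermediate scan is dropped and the next was read against it, the lesions of the dropped interval appear nowhere. If the final scan is dropped, its lesions are lost whatever the reference scan.

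At stake are the T2 and T1 hypointense counts, the proportion free of new or enlarged T2 lesions, and the T2 component of disease-free status. Ignoring a lesion-positive scan can only raise the two proportions.

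**Working it through.** **Window limits.** SAP 2.5.3, Table 5, gives MRI target days 337, 673, 1009 and 1345. Each upper limit is the midpoint of adjacent targets minus 1: (337 + 673)/2 − 1 = 504; (673 + 1009)/2 − 1 = 840; (1009 + 1345)/2 − 1 = 1176. All three match the table.

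**Switchers' EOT scans.** Total time is capped at 192 weeks from randomization (SAP Appendix C, visit-number note), and an MRI is due at EOT (SAP Table 2). For a switch at double-blind Week X, the open-label EOT day is (192 − X) × 7 + 1.

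| Switch week | EOT day | Window | Scheduled scan in window | Result |
|---|---|---|---|---|
| 25–47 | 1170 to 1016 | 841–1176 | day 1009 | EOT scan dropped |
| 73–95 | 834 to 680 | 505–840 | day 673 | EOT scan dropped |

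For Week 80: (192 − 80) × 7 + 1 = 785, which is 785 − 673 = 112 days from target, against 0 for the scheduled scan. At the edge of a range one scan may serve both visits. For other switch weeks the EOT scan is alone in its window or coincides with a scheduled scan.

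**Discontinuers.** An EOT scan on days 338–504 shares the Week 48 window with the day-337 scan. Example: 0 new lesions on day 337 and 4 on day 450 (113 days from target). The rule retains 0 lesions on 1 scan, and the patient is lesion-free.

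**How many switchers (illustration).** I used the planning hazards of 0.4581 and 0.2291 per year (SAP 1.3), with every relapser switching and completing, and no dropout or MRI-driven switches. With S(w) = exp(−h × 7w/365.25):
- placebo: [S(24) − S(48)] + [S(72) − S(96)] = 0.154 + 0.101 = 0.255
- teriflunomide: 0.090 + 0.073 = 0.163

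**Effect on lesion-free status (assumed rates).** Negative binomial with dispersion 1, so P(0) = 1/(1 + μ). Open-label scans only, first interval counted from the first open-label dose.
- Week 80 switcher, mean 1 per 336 days: retained μ = 2, P(0) = 33.3%. Adding the EOT scan, μ = 784/336 = 2.33 and P(0) = 30.0%. Overstatement: 3.3 points. With mean 4: 1/9 = 11.1% against 1/10.33 = 9.7%, or 1.4 points.
- Day-450 discontinuer, mean 1: 1/2 = 50.0% against 1/(1 + 449/336) = 42.8%, or 7.2 points.

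If every switcher in the affected weeks resembled the Week 80 patient at mean 1, the group-level effect would be 0.255 × 3.3 = 0.8 points for placebo-start and 0.163 × 3.3 = 0.5 for teriflunomide-start patients.

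**Transition scan.** For Week 96, Table 4 admits scans on days "589 - Last double-blind dose date + 60 days and before 1st open label dose". SAP Appendix C says "the transition visit will generally coincide with the EOT visit of the double-blind period", with a ±7-day window. An EOT scan done 4 days after the first open-label dose (open-label day 5) fails Table 4 and falls in the open-label Week 48 window. At |337 − 5| = 332 days from target it loses to any scan near day 337. Without such a scan it would be reported as open-label Week 48.

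**Steroid exclusion and the offset.** Take counts of 3, 6 (excluded) and 0. All scans give 9/3 = 3.0 per scan. The SAP gives 3/2 = 1.5. Carrying the 6 forward without changing the offset gives 9/2 = 4.5. If exclusion is unrelated to activity, numerator and offset shrink together and the expected rate is unchanged (1.0 against 1.0 in simulation). Lesion-free status still shifts: with mean 1 per scan and one of two scans excluded, P(0) moves from 1/3 to 1/2.

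**Offset for an added EOT scan.** The Week 80 switcher's three scans cover 336 + 336 + 112 = 784 days, or 784/3 = 261 per scan, against 336 for the two retained. A scan-count offset would lower the per-scan rate to 261/336 = 0.78 of its value. An offset of log time covered would not.

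**The case against.** Several objections stand, and they limit the point.

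- **Reference scan.** The previous-scan notes belong to the switch criteria, and reading is central under a manual not included here. If readers compare with baseline or the last valid scan, lesions on a dropped intermediate scan are recovered. Those on a dropped final scan are not. No reference is stated for new T1 hypointense lesions.
- **T2-free censoring rule.** It speaks of lesions detected by MRI before treatment ends, which could mean any scan. It does not override the general MRI rules, so the ambiguity needs settling.
- **Disease-free status.** A confirmed relapse already fails it, so relapse switchers are unaffected if status runs from randomization. Patients who switch for high MRI activity have likewise already lost T2-free status. The disease-free error therefore falls mainly on patients without relapse who discontinue open label.
- **Exploratory role.** SAP 2.4.4 and 2.4.4.4 draw no confirmatory conclusion from these analyses.

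A reader might infer that steroid exclusion pulls the lesion-rate comparison toward no effect, because 60% of placebo and 36.8% of teriflunomide patients are expected to relapse. The documents do not support this. The protocol bars MRI within 2 weeks of steroids, so the rule catches only deviations. A relapse switcher needs no double-blind EOT visit, and the next scheduled scan is open-label Week 48. Both groups then take teriflunomide. Assuming a 5-day course plus 14 days, the share of scans at risk is 19/336 = 5.7% at the open-label spacing of 48 weeks. The larger 19/168 = 11% belongs to the 24-week double-blind spacing. If scans are rescheduled it is 0%.

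**Conclusion.** The point holds for incident counts. As written, lesions on an unretained scan are not counted. A patient can be wrongly classed as free of new T2 lesions or, without confirmed relapse, sustained progression or Gd-enhancing lesion, as disease-free.

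The firmest case is the open-label EOT scan of patients who switch at about Weeks 25–47 or 73–95, or who discontinue after a scheduled scan in the same window. It needs no protocol deviation and does not depend on the reference scan. The direction for lesion-free status is certain: upward. The size is not. The illustrations suggest a few points among affected patients and about one point or less per group from the switcher route, on assumed lesion rates and adult-based planning hazards.

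The transition case follows from the tables, but its frequency is unknown and it should not be called typical. Steroid exclusion can overstate lesion-free status. It biases the per-scan rate only if exclusion is related to outcome, and neither size nor direction is established.

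**What to change.** Amend SAP 2.4.4.2.3, 2.4.4.2.6 and 2.5.3 before the open-label database lock:

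1. Restrict closest-to-target selection to by-visit summaries and volumes.
2. State the reference scan for new/enlarged T2 and new T1 hypointense counts. Sum these counts over all scans, including EOT. Match the offset to the same scans or, better, use the log of the time they cover, so that carried-forward lesions do not inflate the rate.
3. Use all during-treatment scans for T2-free status and for the T2 component of disease-free status. State that the EOT scan qualifies, since the flow charts define EOT as the first visit after the last dose.
4. Keep the steroid exclusion for Gd-enhancing lesions.
5. Assign a Week 96/EOT scan done within the ±7-day visit window to double-blind Week 96, even if open-label dosing has begun, in agreement with the separate double-blind SAP.

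The cost is wording, derivation code and one offset term. No new scans are needed, and no re-reads if the reference is the previous scan. The downside is small: a lesion enlarging on two successive scans may count twice, and a few T2 counts will come from steroid-exposed scans.
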